8.4. Multiple Comparisons and Multiplicity

The overall family-wise Type I error rate will be controlled by a hierarchical (gatekeeping) testing procedure.

The surrogate efficacy endpoint (UP/C response at Week 36) will first be tested at the interim analysis at 2-sided $\alpha = 0.05$. If the test is not significant, hypothesis testing stops. If the test is significant, then the following country-specific hierarchical testing will be performed.

For non-US countries, the hierarchy for the hypothesis testing will be as follows, if the test of the surrogate efficacy endpoint (UP/C response at Week 36) is significant:

1. test the primary efficacy endpoint (eGFR chronic slope over 2 years) at the final analysis at 2-sided $\alpha = 0.05$. If the test is not significant, hypothesis testing stops. If the test is significant,

2. test the 3 secondary endpoints using a Bonferroni-Holm procedure to control for family-wise error rate at 2-sided $\alpha = 0.05$.

For the US, the hierarchy for the hypothesis testing will be as follows, if the test of the surrogate efficacy endpoint (UP/C response at Week 36) is significant:

1. test the primary efficacy endpoint (eGFR total slope over 2 years) at the final analysis at 2-sided $\alpha = 0.05$. If the test is not significant, hypothesis testing stops. If the test is significant,
2. test the efficacy endpoint of eGFR chronic slope over 2 years at the final analysis at 2-sided $\alpha = 0.05$. If the test is not significant, hypothesis testing stops. If the test is significant,
3. test the efficacy endpoint of change in eGFR from baseline of the double-blind period to 4 weeks post-cessation of randomized treatment at Week 112 at the final analysis at 2-sided $\alpha = 0.05$.

For planned statistical tests that are not formally performed as a result of the aforementioned multiplicity adjustment strategy, nominal 2-sided p-values (without adjustment for multiplicity) will be computed as a measure of the strength of association between the endpoint and the treatment effect rather than formal tests of hypothesis.

8.5. Analysis of the Primary Efficacy Endpoint

8.5.1. Primary Efficacy Analysis

8.5.1.1. eGFR Chronic Slope over 2 Years

The primary efficacy analysis will be based on the FAS. The eGFR chronic slope over 2 years, defined as the slope of eGFR following the initial acute effect of randomized treatment (ie, Week 6 to Week 108), will be analyzed via a mixed-effects model with linear spline (ie, a 2-slope model with knot or change point at Week 6) with available eGFR data at the final analysis. The response variable is the eGFR measured at on-treatment, post-baseline assessments during the randomized treatment period for each patient. The model will include the following fixed effects:

- Treatment group (2 levels: sparsentan, irbesartan)
- Baseline eGFR
- Time from baseline (analysis visit, in weeks)
- Time from change point (in weeks)
- Treatment group by time from baseline interaction
- Treatment group by time from change point interaction
- Randomization stratification variable (4 levels based on Screening eGFR and UP/C)

In addition, the model will also include a random intercept and random slopes (time from baseline and time from change point) for each patient. The mixed model will utilize restricted maximum likelihood estimation with Kenward-Roger method to compute the denominator

degrees of freedom for tests of fixed effects. An unstructured covariance matrix will be assumed. If convergence issues arise, the autoregressive-1 covariance structure will be used.

The associated slope estimates within treatment group, difference in slopes, 95% CI, and 2-sided p-value will be extracted from the model. The treatment effect for the slope following the change point at Week 6 (ie, difference in slopes) will be the sum of the coefficients for the treatment group by time from baseline interaction and treatment group by time from change point interaction estimated from the model. Slope and the difference in slopes will be annualized for ease of presentation and interpretation.

8.5.1.2. eGFR Total Slope over 2 Years

The primary efficacy analysis will be based on the FAS. The eGFR total slope over 2 years, defined as the slope of eGFR following the initiation of randomized treatment (ie, Day 1 to Week 108), will be analyzed via a mixed-effects model with available eGFR data at the final analysis. The response variable is the eGFR measured at on-treatment, post-baseline assessments during the randomized treatment period for each patient. The model will include the following fixed effects:

- Treatment group (2 levels: sparsentan, irbesartan)
- Baseline eGFR
- Time from baseline (analysis visit, in weeks)
- Treatment group by time from baseline interaction
- Randomization stratification variable (4 levels based on Screening eGFR and UP/C)

In addition, the model will also include a random intercept and random slope for each patient. The mixed model will utilize restricted maximum likelihood estimation with Kenward-Roger method to compute the denominator degrees of freedom for tests of fixed effects. An unstructured covariance matrix will be assumed. If convergence issues arise, the autoregressive-1 covariance structure will be used.

The associated slope estimates within treatment group, difference in slopes, 95% CI, and 2-sided p-value will be extracted from the model. The treatment effect will be the contrast between sparsentan and irbesartan marginal slope estimates. Slope and the difference in slopes will be annualized for ease of presentation and interpretation.

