6. INVESTIGATIONAL PLAN

6.1. Endpoints

6.1.1. Efficacy Endpoints

6.1.1.1. Primary Efficacy Endpoint

The primary efficacy endpoint is the slope of eGFR over approximately 2 years of randomized treatment assessed at the final analysis. The slope of eGFR is evaluated following the initial acute effect of randomized treatment (ie, from Week 6 to Week 108; chronic slope over 2 years) in non-United States (US) countries and following initiation of randomized treatment (ie, from Day 1 to Week 108; total slope over 2 years) in the US.

The surrogate efficacy endpoint is the proportion of patients achieving a UP/C ≤ 1.5 g/g (170 mg/mmol) and a $>40\%$ reduction from baseline of the double-blind period in UP/C at Week 36.

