6.3. Patient Completion and Overall Study Completion

6.3.1. Patient Completion of the Double-Blind Period

Each patient will participate in the double-blind period of the study for approximately 6 weeks during the screening phase, followed by 108 weeks of double-blind treatment. At the end of the 108-week treatment period, study medication will be discontinued and replaced with standard-of-care therapy treatment, including treatment with RAAS inhibitors provided there are no contraindications for their use. If the patient was treated with irbesartan at study entry, an alternative ARB at an equivalent dose is required from Week 108 to Week 112. The Investigator may make additional adjustments in antihypertensive medications as necessary to adequately control the patient's blood pressure.

Patients will return to the site for the final (Week 112) visit 4 weeks later. Thus, patients will participate in the double-blind period for a total of approximately 118 weeks or about 30 months.

A patient will be considered as having completed the double-blind period, regardless of whether the patient is on or off study medication, if the patient is followed until Week 112. The need for additional intervention for the treatment of FSGS or the occurrence of safety endpoints do not constitute completion of the double-blind period and are not criteria for withdrawal from the study or study medication.

Patients who successfully complete the final Week 112 Visit will complete the assessments listed in the schedule of events ([Section 15.1](#)). Patients who received blinded study medication throughout the duration of the double-blind period (ie, did not permanently discontinue study medication) may be eligible to enroll in the open-label extension (see [Section 7.2](#)).

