6.4.2. Permanent Discontinuation of Study Medication

During the course of this long-term study, it is anticipated that patients may permanently discontinue study medication (sparsentan or irbesartan) for any of the following reasons:

- Receipt of kidney transplant or initiation of RRT
- Any SAE, AE of interest (AEOI; see [Section 10.3](#)), clinically significant laboratory abnormality, intercurrent illness, or other medical condition that indicates to the Investigator that continuation on study medication is not in the best interest of the patient
- Significant protocol deviation (ie, patient failed to meet entry criteria or did not comply with protocol requirements resulting in an unacceptable risk to the patient's health)
- Investigator discretion
- Patient (or parent/legal guardian) decision to stop study medication
- Patient pregnancy
- Diagnosis of Class II-IV CHF
- Hyperkalemia resistant to treatment (see Appendix B, [Section 15.2.2](#) for hyperkalemia management guidelines)
- Termination of the study by the Sponsor, US Food and Drug Administration (FDA), or other regulatory authorities (see [Section 13.4.5](#))
- Lost to follow-up

Therapy to treat relapse (that is a new or substantial change in immunosuppression) during the study is not a reason for permanent study medication discontinuation.

Patients who permanently discontinue study medication during the double-blind period should be encouraged to continue study visits through Week 112 for continued collection of safety and efficacy data despite stopping study medication, but may withdraw consent at any time (see [Section 6.5](#)). Patients who agree to continue regularly scheduled study visits will complete the End of Treatment (EOT) assessments listed in the schedule of events ([Section 15.1](#)) as close as possible to the patient's last dose of study medication. The visit data, including the primary reason for discontinuation of study medication, will be recorded on the EOT electronic case report form (eCRF). Subsequent study visit data will be recorded on the visit-specific eCRF, and the patient's final study visit will be recorded on the End of Study (EOS) eCRF.

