12.7.1. Primary Efficacy Analysis

12.7.1.1. Primary Efficacy Endpoint: Slope of eGFR at the Final Analysis

For the primary endpoint of slope of eGFR evaluated following the initial acute effect of randomized treatment (ie, from Week 6 to Week 108; chronic slope over 2 years), a mixed-effects model with linear spline (knot or change point at Week 6) will be fitted to the available eGFR data. The response variable is the eGFR measured at post-baseline assessments for each patient during the double-blind period. The model will include fixed effects for treatment, both stratification factors for randomization, baseline eGFR (continuous), time (in weeks) from baseline (continuous), and time (in weeks) from the change point (ie, $\text{timek} = \max(\text{time} - 6, 0)$), time-by-treatment, and timek-by-treatment interactions. The model will also include a random intercept and random slopes (time and timek) for each patient. The mixed model will utilize restricted maximum likelihood (REML) estimation with Kenward-Roger method used to compute the denominator degrees of freedom for tests of fixed effects. The model will assume an unstructured covariance matrix. If the model does not converge under the unstructured covariance matrix, the autoregressive-1 covariance structure will be used.

The primary efficacy hypothesis of interest is whether eGFR slopes over the blinded treatment period (after adjusting for early hemodynamic effects) are different between the 2 treatment groups, ie:

$$H_0: (\beta_{\text{time}*\text{treatment}} + \beta_{\text{timek}*\text{treatment}}) = 0 \text{ versus:}$$

$$H_1: (\beta_{\text{time}*\text{treatment}} + \beta_{\text{timek}*\text{treatment}}) \neq 0.$$

This hypothesis will be tested using the mixed model by testing whether the time-by-treatment interaction parameters least-squares (LS) mean estimate is equal to 0.

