5.4. Changes from Planned Protocol Analyses

The analyses specified in this SAP are consistent with DUPLEX Protocol Amendment 6 with the following exception.

The primary statistical evaluation of the surrogate endpoint, FPPE, will be performed using the Interim Analysis Set (IAS) rather than the subset of patients in the FAS who are scheduled to have completed their Week 36 visit per Section 12.11 of the protocol. Statistical evaluation of FPPE using the subset of patients in the FAS who are scheduled to have completed their Week 36 visit will be performed as a sensitivity analysis.

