6.5.4. Visit Windows

A visit window method will be applied to determine analysis visits across the study for efficacy and safety endpoints based on laboratory results, including eGFR and quantitative urinalysis (including UP/C and FPFE). If a patient has multiple assessments (including unscheduled visits) within a visit window, the value closest to the target day for that visit will be selected for analysis. If more than 1 assessment is equidistant to the target day, then the latest value will be selected. For efficacy analysis visits on or prior to Week 108, only assessments while the patient is on randomized treatment should be included (see [Section 8.1](#) for definition of on treatment).

For quantitative urinalysis endpoints that are derived as the geometric mean of replicates collected over several days, all replicates used to derive the average should be mapped to the same analysis visit per Table 2, should be within 5 days of each other, and should all have been collected while the subject was on study medication. For the derivation of baseline, all replicates must have been collected on or prior to the date of reference dose. The study day of the endpoint will be derived as the maximum study day of the replicates used in the derivation.

If a patient is missing a UP/C assessment at a given analysis visit due to only having 1 urine sample available within 5 days, the available single assessment closest to the target day for that visit will be selected for sensitivity analysis.

The following visit windows for the double-blind period are defined for endpoints based on laboratory results. Visit windows for the OLE will be defined in a separate SAP.

Table 2: Visit Windows (Study Days)

Analysis Visit	Relative Target Day	Analysis Visit Window (Study Days)	
		eGFR and Safety Labs	Quantitative Urinalysis
Week 2	15	2 – 22	N/A
Week 4	29	23 – 36	N/A
Week 6	43	37 – 50	2 – 71
Week 8	57	51 – 71	N/A
Week 12	85	72 – 127	72 – 127
Week 24	169	128 – 211	128 – 211
Week 36	253	212 – 295	212 – 295
Week 48	337	296 – 379	296 – 379
Week 60	421	380 – 463	380 – 463
Week 72	505	464 – 547	464 – 547
Week 84	589	548 – 631	548 – 631
Week 96	673	632 – 715	632 – 715
Week 108 ¹	757	716 – 771	716 – 771
Week 112 ¹	785	>771	>771
4-week after EOT ²	785 ¹ or Last Dose Date + 28 ³	>771 ¹ or 2-12 weeks (14-84 days) after Date of Last Dose ³	>771 ¹ or 2-12 weeks (14-84 days) of Date of Last Dose ³

¹ For patients who completed the planned randomized treatment period.

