8. EFFICACY

8.1. General Considerations

All efficacy analyses will be based on the FAS or IAS, as described below. The primary, surrogate, and secondary endpoint analyses will also be performed on the PP Analysis Set as supportive analyses. All primary efficacy analyses based on laboratory data will use central lab data only. All efficacy analyses specified below refer to the double-blind period only.

UP/C will be determined using first morning void urine samples and will be calculated as the geometric mean of 3 first morning void urine samples collected within 5 days prior to the visit. If one of the samples is missing, the average of the other 2 samples will be used. As UP/C is a highly right-skewed variable, analyses will be performed on log-transformed data. For ease of interpretation, results will be presented in the original units.

The eGFR for each baseline and post-baseline visit will be determined using the CKD-EPI (Levey 2009) formula for patients ≥ 16 years of age at the time of screening and the Modified Schwartz formula for patients < 16 years of age at the time of screening (Schwartz 2009a; Schwartz 2009b).

For the purposes of efficacy analyses, an assessment is considered “on treatment” if it occurs after the first dose of study medication and no more than 3 days after the date of last dose of randomized treatment.

For all least-squares (LS) means that include strata coefficients, the observed strata proportions will be used instead of assuming equal sizes of strata.

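### The SAP restricts both primary slope models to on-treatment eGFR, does not declare this as a change from the protocol, and states no slope analysis that uses eGFR measured after patients stop drug

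*SAP*

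**What the plan says.** **SAP.** Sections 8.5.1.1 (chronic slope) and 8.5.1.2 (total slope) use the same sentence: "The response variable is the eGFR measured at on-treatment, post-baseline assessments during the randomized treatment period for each patient". Section 8.1 counts an assessment as on treatment if it falls after the first dose and "no more than 3 days after the date of last dose of randomized treatment". Section 6.5.4 applies the limit to every efficacy visit up to Week 108: "For efficacy analysis visits on or prior to Week 108, only assessments while the patient is on randomized treatment should be included".

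**Protocol.** Section 12.7.1.1 describes the same two models with a different data set: "The response variable is the eGFR measured at post-baseline assessments for each patient during the double-blind period". Section 6.3.1 makes that period independent of drug intake: "A patient will be considered as having completed the double-blind period, regardless of whether the patient is on or off study medication", provided follow-up reaches Week 112. Section 6.4.2 says that patients who permanently stop "should be encouraged to continue study visits through Week 112 for continued collection of safety and efficacy data despite stopping study medication".

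**Declared changes.** SAP 5.4 states: "The analyses specified in this SAP are consistent with DUPLEX Protocol Amendment 6 with the following exception". The single exception is the population for the interim test of the surrogate endpoint.

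**The concern.** A patient who stops drug at Week 36 and attends every later visit contributes eGFR to Week 108 under the protocol's model text, but only to about Week 36 under the SAP. The two documents therefore define the primary data set differently, and the section of the SAP meant to list such differences does not mention it.

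The choice also decides what the result means. An on-treatment slope describes the course while patients take the drug. A slope from all observed values describes the course after assignment, including what happens once drug is stopped. The first can serve as the primary analysis. The gap is that, on the natural reading of the SAP, every planned check of the slope rests on on-drug values or on assumed values after stopping. The trial would collect eGFR after discontinuation and never show whether the slope result holds when it is included.

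**Working it through.** **1. Do the planned slope checks use observed off-drug eGFR?** SAP 8.5.2 item by item:

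| Analysis | Treatment of eGFR after stopping |
|---|---|
| Multiple imputation (6.6.1.2.1) | Imputes missing values after a discontinuation event. Stopping randomized therapy is such an event, listed separately from dropout. Not stated that measured values are kept |
| Tipping point (6.6.1.2.2) | Shifts the imputed values; covers jump-to-reference and worse, by assumption |
| Treatment completers | Removes patients who stopped |
| Local laboratory data, knot at Week 4 or 8, immunosuppressant change, per protocol | Repeat the on-treatment model |

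Elsewhere, off-drug eGFR from early discontinuers is stated to enter only the sensitivity analyses at 4 weeks after end of treatment for the Week 112 endpoints (8.7.2, 8.7.3), with one value per patient and no slope. The by-visit model of absolute change to Week 112 (8.8.1.3) does not fill the gap, because Table 2 reserves the Week 112 window for patients who completed treatment. Safety summaries use on-study data.

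**2. The plan's own power figure.** For the total slope: 150 per arm, difference 2.1, SD 5.50, two-sided 0.05. SE = 5.50 × √(2/150) = 0.635. Power = Φ(2.1/0.635 − 1.96) = 91.1%, which agrees with the stated figure of at least 90%. This SE is the yardstick for the total slope below.

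**3. How many values are at stake.** Scheduled post-baseline visits are Weeks 2, 4, 6, 8, 12, then every 12 weeks to 108: 13 values. Assumptions: 10% to 30% of 300 patients stop, at times uniform over 108 weeks, and attend every later visit.

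- Expected values after stopping, per stopper: sum of visit weeks / 108 = 560/108 = 5.19 of 13. For Weeks 60 to 108: 420/108 = 3.89 of 5.
- All visits: 30 × 5.19 = 156 to 90 × 5.19 = 467, out of 300 × 13 = 3,900 (4% to 12%).
- Weeks 60 to 108: 30 × 3.89 = 117 to 90 × 3.89 = 350, out of 300 × 5 = 1,500 (8% to 23%).

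These are upper limits. If half of the off-drug visits are attended, 156 to 467 becomes 78 to 233.

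**4. What the slope could become.** Suppose the difference accrues at 2.1 per year (total) or 2.52 per year from Week 6 (chronic) until stopping, then at 0, with an optional step in eGFR on stopping sparsentan. With complete visits, the random-coefficient slope equals the ordinary least-squares slope, so the variance components drop out. For stopping share p and step d in mL/min/1.73 m²:

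- Total = 2.1 × (1 − 0.469p) + 0.483 × p × d
- Chronic = 2.52 × (1 − 0.496p) + 0.483 × p × d

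The factors 0.469 and 0.496 come from regressing the mean path on the 13 visit times, with a knot at Week 6 for the chronic slope. The factor 0.483 is 52.18/108.

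| Step d | Total, p = 10 / 20 / 30% | Chronic, p = 10 / 20 / 30% |
|---|---|---|
| 0 | 2.00 / 1.90 / 1.80 | 2.39 / 2.27 / 2.14 |
| +3 | 2.15 / 2.19 / 2.24 | 2.54 / 2.56 / 2.58 |
| +5 | 2.24 / 2.39 / 2.53 | 2.64 / 2.75 / 2.87 |
| −5 | 1.76 / 1.42 / 1.08 | 2.15 / 1.79 / 1.42 |

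Break-even step: 2.1 × 0.469/0.483 = 2.04 (total) and 2.52 × 0.496/0.483 = 2.59 (chronic). The on-treatment total-slope model, simulated with stopping independent of outcome, gave 2.12, 2.08 and 2.11 at the three rates, so it stays near 2.1. The chronic comparator is the planning value of 2.52 and was not simulated.

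With no step, the total slope moves by 0.10 to 0.30, or 0.16 to 0.47 SE. At the worst corner it moves by 2.1 − 1.08 = 1.02, or 1.6 SE.

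**The case against.** The strongest reply is that the protocol's wording is loose and the SAP had to narrow it. The double-blind period runs to Week 112, four weeks after planned cessation, so taken literally it would feed off-drug Week 112 values into a slope that ends at Week 108. The endpoint itself points towards treatment: "The primary efficacy endpoint is the slope of eGFR over approximately 2 years of randomized treatment assessed at the final analysis". The hypotheses in 12.7.1.1 also concern slopes over the blinded treatment period. This stands as far as it goes: the protocol states no estimand and can be read either way. It is a reason to reconcile the texts, and it does not explain why SAP 5.4 is silent.

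Second, the SAP does address discontinuation. The tipping point reaches jump-to-reference and beyond, and the imputation text can be read as keeping measured off-drug values because it imputes only what is missing. The first part is true, but it works by assumption where measurements may exist. The second reading is possible, but the rule in 6.5.4 covers all efficacy visits to Week 108 and points the other way.

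Third, patients who stop resume standard of care (Protocol 6.4.2), so off-drug values mix withdrawal with new therapy. That supports an on-treatment primary analysis. It does not support leaving those values out of every slope analysis.

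Fourth, SAP 5.4 refers to Amendment 6, while the protocol supplied is Amendment 9. Its history lists no change to the primary analysis in Amendments 7 to 9, though it mentions minor consistency edits in 7 and 8. That the wording is unchanged is a reasonable inference that cannot be checked directly.

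**Conclusion.** The concern holds and should be fixed. Both primary slope models exclude eGFR taken more than 3 days after the last dose, the protocol's model text has no such limit, the difference is undeclared, and no slope analysis is stated to use observed off-drug values. Read literally, the definition still counts values taken during a temporary interruption, so the limit bites after permanent discontinuation.

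Neither the size nor the direction of the effect can be fixed from the documents. The stopping rates, the uniform timing, full attendance after stopping and the ±5 steps are all assumptions, and the step is applied to sparsentan stoppers only although treatment changes in both arms. If benefit simply ends at stopping, the change is below half an SE for the total slope. It exceeds one SE only when a large step is combined with frequent stopping. That justifies a correction to the plan without making the on-treatment primary analysis invalid.

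**What to change.** 1. Reconcile Protocol 12.7.1.1 with SAP 8.5.1.1 and 8.5.1.2 on the response variable. If the on-treatment restriction remains primary, declare it in SAP 5.4.
2. Add to SAP 8.5.2 a named sensitivity analysis of both the chronic and the total slope: same models, all observed central-laboratory eGFR to Week 108 regardless of treatment discontinuation, explicitly exempt from the on-treatment rule in 6.5.4 and 8.1.
3. Add a version of the imputation and tipping-point analyses that keeps observed off-treatment values and imputes only values that are truly missing, and say so in 6.6.1.2.1.
4. Report by arm how many off-drug eGFR values the primary model excludes.

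The cost is wording in both documents and one extra set of model runs on data already collected. The added estimate mixes on-drug and off-drug values and may be less favourable. It sits beside the primary analysis and does not replace it.
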